## INTRODUCTION

The number and complexity of gastrointestinal (GI) procedures is increasing rapidly [1]. Over 50 million GI endoscopic procedures were performed in the United States alone in 2017, including approximately 19 million colonoscopies [2]. The complexity of endoscopic procedures has increased, By using this technique, a patient can get both advantages such as Therapeutic and Diagnostic. ERCP technique even made this procedure easier for patients who were at the high risk in conventional surgery [10]. It became a challenge for using the anesthetic technique with the changing status of patient periodically, in most of the cases sedation is widely used. Although it is a risky procedure, for that general anesthesia is necessary because of patients who are undergoing ERCP in Co-morbidities [7] Propofol is widely used agent for sedation for GI endoscopy [6]. Advantages of propofol include its rapid effect site equilibration and short elimination half-time even after prolonged infusion. Thus, the depth of sedation can be adjusted rapidly, and patients recover quickly without residual psychomotor effects. However, propofol has a narrow therapeutic index, meaning that patients may rapidly transition to deeper levels of sedation, including general anesthesia, and apnea, airway obstruction, hypoxemia and/or hypotension can result. Thus, propofol should be titrated to effect, and administered by clinicians who are able to manage airway and hemodynamic compromise. Sevoflurane is relatively new inhaled anesthetic that also permits rapid emergence due to its low blood solubility. It has been successfully used as an alternative to propofol for various day care procedures.

## OPERATIONAL DEFINATIONS

### SEDATION

. A drug induced depression of consciousness during which patient can not be aroused easily but respond purposefully following repeated or noxious stimulation

### RECOVERY TIME

- Time period from cessation of drugs to regain consciousness (Orientation to time and place)

## **OBJECTIVE**

The aim of the study is to find out the comparison between two drugs of moderate sedation in patients undergoing ERCP. One drug is propofol and another one is sevoflurane. Both agents will be compared regarding sedation, hemodynamic changes in patients undergoing ERCP. For sedation we use Ramsay Sedation score.

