## **DATA COLLECTION PROCEDURE**

This study will be conducted after approval of ethical committee of SIUT. For research 86 patients will be selected for the elective ERCP. Pre-operative assessment will be taken such as history of patients, general physical examination, systematic examination, and laboratory investigations will be part of assessment. Patients will be divided in two groups based on agents used for the research study. Both the groups will be induced by injection midazolam 0.06 mg/kg and injection nalbuphine 0.1 mg/kg . Anesthesia will be maintained in.....

**Group A** Sevoflurane inhalation to achieve MAC Amnesia 0.25%.

**Group B** Propofol infusion at 50 ug/Kg/min.

When Ramsay Sedation Scale **5** is achieved than surgeon will be allowed to insert endoscope. Inj **Ketamine** 0.5mg/kg will be used for Rescue sedation .Upon arrival in operation theatre standard monitoring which includes pulse oxymeter (SPO2), noninvasive blood pressure (NIBP), electrocardiogram (ECG) electrodes will be applied, and baseline readings will be recorded. After that venous access will be secured on a non-dominant hand by 20G IV cannula, i/v fluid (R/L or N/S) will then be started by 8 ml/kg/h and O2 will be given by nasal mask at 4 L/min. All baseline parameters will be taken, after that readings will be taken at 5 min, 10 min, 15 min,20 min and so on till procedure ends.

Complications such as respiratory depression, coughing, gagging, nausea and vomiting will be recorded during the procedure and treated accordingly. If SpO2 goes down below 92% for more than 10 seconds or patient develops apnea, it will be considered oxygen desaturation.

It will be managed by O2 inhalation and supporting airway. A heart rate under 40beats per minute will be considered bradycardia and it will be managed by inj Atropine 10 ug/Kg I/V. Mean arterial pressure level that is lower than 60 mmHg or 20% less than the baseline will be regarded as hypotension and it will be managed by fluid bolus or vasopressors.

Complications such as respiratory depression, coughing, gagging, nausea and vomiting will be recorded and treated accordingly. After the procedure, patient will be awakened and shifted to HDU.

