#### **DATA ANALYSIS:**

For data analysis SPSS software will be used of version 22. Mean and standard deviation will be computed for variable such as age, height, BMI, RSS, HR, SBP, DBP and MAP at 0,1,3,5,10 min. For determining the differences in the hemodynamics mean unpaired “t” test will be used between groups. Categorical Variables such as gender, ASA and post op complications like gagging, PONV, Apnea and cough will be presented as frequencies and percentages.

Chi-square test will be followed and used between 2 groups, there proportion difference will be compared using P value

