## PERFORMA

GROUP A  GROUP B 

CASE#	
DATE	
Serial #	
AGE	YEARS
SEX	MALE    FEMALE
WEIGHT	KG
HEIGHT	Cm
MALAMPATI SCORE	
ASA	
BMI	Kg/m 

Time in min	Haemodynamic Monitoring			Respiratory Monitoring			Sedation monitoring	
	HR b/n	SBP mmHg	DBP mmHg	MAP mmHg	SpO2%	R/R/min	END TIDAL CO2	Ramsay sedation score
Base line								
5 min								
10 min								
15 min								
20 min								
25 min								
30 min								
35 min								
40 min								
45 min								
50 min								
55 min								
60 min								

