## COMPLICATION DURING AND AFTER ERCP

DURING PROCEDURE	YES	NO
APNEA		
COUGH		
GAGGING		
POST-OPERATIVE NAUSEA AND VOMITING		

Ketamine used as Rescue Sedation	Yes	No	Number of doses given
----------------------------------	-----	----	-----------------------

RECOVERY TIME	MINUTES
---------------	---------

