Comparison between inhalational anesthetic (sevoflurane) and intravenous anesthetic (propofol infusion) for maintenance of sedation during Endoscopic retrograde cholangiopancreatography

Principle investigator

[name]

Senior Lecturer

Department of Anesthesiology SIUT Karachi

Dated: 01-07-2021

DATA ANALYSIS:

For data analysis SPSS software will be used of version 22. Mean and standard deviation will be computed for variable such as age, height, BMI, RSS, HR, SBP, DBP and MAP at 0,1,3,5,10 min. For determining the differences in the hemodynamics mean unpaired “t” test will be used between groups. Categorically Variables such as gender, ASA and post op complications like gagging, PONV, Apnea and cough will be presented as frequencies and percentages.

Chi-square test will be followed and used between 2 groups, there proportion difference will be compared using P value

(Note: This plan is a part of synopsis which we have uploaded on NCT form)

Monday, August 30, 2021
ERC Number: 325

Approval No: SIUT-ERC-2021/A-325

Approval Issued: August 30, 2021

[name]
Department of Anesthesia, SIUT

Re: Project Title “Comparison between inhalational anesthetic (sevoflurane) and intravenous anesthetic (propofol infusion) for maintenance of sedation during Endoscopic retrograde cholangiopancreatography.”

[figure not shown]
Dear [name],

Thank you for submitting the above referenced protocol to the SIUT-Ethical Review Committee (ERC). ERC finds that this protocol raises no ethical concerns. Approval is granted and you may commence your research. According to SIUT-ERC requirements, the ERC approval number should be clearly printed and visible on all consent forms used in the study.

Please note that this approval is valid for one year and relates to the ethical content of the study only. If you make any changes to the protocol during the period of this approval, you must submit a revised protocol to the SIUT-ERC for approval before implementing the changes.

SIUT-ERC requires a follow up from all researchers about the status of the approved research at the completion of one year from the date of issuance. You are also expected to comply with this practice.

Yours Sincerely,

[name], DABIM, DABP, DAB Nephrology
Professor and In charge Pediatric Nephrology,
Co-Chair, SIUT-Ethical Review Committee (SIUT-ERC)

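### Sedation by Ramsay score is a stated comparison, but no between-group test is named for it, the analysis times do not match the recording form, and ketamine rescue is not named in the analysis

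*Protocol*

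**What the plan says.** The protocol's Objective sets two comparisons: "Both agents will be compared regarding sedation, hemodynamic changes in patients undergoing ERCP". It then fixes the sedation measure: "For sedation we use Ramsay Sedation score".

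The Data Analysis section, repeated almost word for word in the SAP, asks for means and SDs of "RSS, HR, SBP, DBP and MAP at 0,1,3,5,10 min". The only test it gives for continuous measures opens "For determining the differences in the hemodynamics mean unpaired" and is tied to haemodynamics. The chi-square sentence is general and names no variable. The categorical variables offered as examples are gender, ASA class and four complications; neither RSS nor ketamine is among them.

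On timing, the Data Collection Procedure says that after baseline "readings will be taken at 5 min, 10 min, 15 min,20 min and so on till procedure ends". That sentence does not name RSS. The Performa does: its "Ramsay sedation score" column sits on the same 5-minute grid, with rows to 60 min.

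On rescue, the Data Collection Procedure states that ketamine "0.5mg/kg will be used for Rescue sedation". The complications form has an item "Ketamine used as Rescue Sedation", with yes/no and the number of doses.

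**The concern.** Three gaps meet in one stated objective.

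- **No test.** With no RSS test, time point or patient-level summary named, the sedation comparison could be chosen after the data are seen.
- **Wrong times.** The analysis calls for readings that the form does not hold, and its means stop at 10 min. The trial is about maintenance of sedation, and most of that period falls after 10 min in any procedure of ordinary length on this form. The same list governs the means of heart rate and of systolic, diastolic and mean arterial pressure, which bear on the stated hypothesis.
- **Rescue not named.** Ketamine is given to deepen sedation. If one agent sedates less well and its patients receive more ketamine, recorded RSS can look similar in the two arms. RSS 5 must also be reached before endoscope insertion in both arms, which pulls the scores together further. Similar RSS then cannot be read as similar sedation unless rescue is shown beside it.

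**Working it through.** **1. The plan's own figure.** The only sample-size figure is for hypotension: 33% v 8.8%, 80% power, 5% level, 43 per arm (Sample size). Sidedness is not stated; two-sided is assumed. With pooled variance and mean proportion (0.33 + 0.088)/2 = 0.209:

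n = [1.960 × √(2 × 0.209 × 0.791) + 0.842 × √(0.33 × 0.67 + 0.088 × 0.912)]² / (0.242)² = (1.127 + 0.462)² / 0.0586 ≈ 43.1, or 44 rounded up.

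Power at 43 per arm is 79.9%. The figure reproduces to within one patient per arm. It does not involve RSS, so nothing below changes it.

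**2. Times side by side** (time 0 taken as baseline).

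| | Times (min) | Count |
|---|---|---|
| Analysis list | 0, 1, 3, 5, 10 | 5 |
| Form rows | 0, 5, 10, …, 60 | 13 |
| In both | 0, 5, 10 | 3 |
| In analysis, no form row | 1, 3 | 2 |
| On form, not in the means | 15 to 60 | 10 |

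After baseline, the means use 2 of 6 readings in a 30-min procedure (33%), 2 of 8 in 40 min (25%) and 2 of 12 in 60 min (17%). The documents give no expected duration, so these three lengths show a range.

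**3. What each measure is assigned.**

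| Measure | Recorded | Summary named | Between-group test named |
|---|---|---|---|
| HR, SBP, DBP, MAP | Every 5 min | Mean, SD to 10 min | Unpaired t-test |
| RSS | Every 5 min | Mean, SD to 10 min | None |
| Ketamine yes/no | Yes | None | None by name; could fall under chi-square |
| Ketamine doses | Yes | None | None |

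**4. How much masking could matter.** The documents give no RSS SD or expected difference, so this is an illustration only. Assume a true difference of 0.5 points, 43 per arm, two-sided 5%, and treat RSS as roughly normal:

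power ≈ Φ(δ / (σ√(2/43)) − 1.96)

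| Assumed SD | δ = 0.5 | δ = 0.25 (half masked by rescue) |
|---|---|---|
| 0.5 | 99.6% | 64.0% |
| 0.75 | 87.1% | 33.9% |
| 1.0 | 64.0% | 21.2% |

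**5. Why a patient mean over all readings is not a safe remedy.** Suppose a patient scores 3 at 5 min and 5 thereafter. The mean is (3 + 5 × 5)/6 = 4.67 over 6 readings and (3 + 8 × 5)/9 = 4.78 over 9. With 3 at both 5 and 10 min it is (6 + 20)/6 = 4.33 against (6 + 35)/9 = 4.56. The same early course gives different means merely because procedures differ in length. The mean also cancels: RSS 4 and 6 in equal halves averages 5, and so does RSS 4/5/6 in proportions 10/80/10%.

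**The case against.** The strongest reply has four parts.

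- **Later readings are used.** A reader might infer that everything recorded from 15 min on has no purpose. The documents do not support that. The Data Collection Procedure defines hypotension, bradycardia and desaturation from blood pressure, heart rate and SpO2 without a time limit, and hypotension is the sample-size outcome. The time list sits only in the mean-and-SD sentence. The loss is therefore to the RSS and haemodynamic means, not to event detection. This part of the reply stands.
- **Rescue may already be covered.** A reader might infer that ketamine is excluded from analysis. The variable lists are open-ended and the chi-square sentence is general, so yes/no rescue could be read into it. That stands. Number of doses cannot be read in, and nothing links rescue to the interpretation of RSS.
- **Sedation is secondary.** The hypothesis and the sample size are haemodynamic. That stands, and it limits the consequence. It does not remove a comparison that the Objective states in plain terms.
- **Comparing rescue beside RSS is not an adjustment.** This is correct. The form has no field for the time of each dose, so readings before and after ketamine cannot be separated from it. The protocol also states no criterion for giving ketamine, so the rescue comparison has limits of its own. It is still the least that makes the RSS result interpretable.

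**Conclusion.** The point holds for the sedation objective and for the haemodynamic means. By direct count, 2 of 5 analysis times have no form row and 10 of 13 form rows are outside the planned means. RSS has no named between-group test. Ketamine is recorded but not named in the analysis. None of this needs an assumption beyond taking time 0 as baseline.

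That rescue can hide an RSS difference is reasoning, not a figure in the documents. The power table shows what halving an assumed difference would do across a range of assumed SDs; it does not predict this trial.

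A reader might go further and conclude that the powered comparison or the sample size is undermined. The documents do not support that: N rests on hypotension and reproduces. The matter should be corrected because a stated objective cannot be reliably answered as planned and the listed times cannot be followed from the form.

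**What to change.** Make the same edits in the protocol's Data Analysis section and in the SAP.

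1. Replace the list of analysis times with the recorded ones (baseline, then every 5 min to the end of the procedure) for RSS, HR, SBP, DBP and MAP, and show the number of patients at each time. State that the longer list is descriptive, so that it does not become a t-test at every row.
2. Name one between-group RSS comparison in advance. It should use the recorded post-baseline readings and respect the ordinal scale and unequal procedure lengths, for example a rank-based or ordinal comparison over a fixed window of times that most patients reach. Report counts per RSS category by arm, so that over- and under-sedation do not cancel unseen. Do not present a patient mean over all readings as protected from procedure length.
3. Compare ketamine rescue (yes/no) by arm with chi-square, or Fisher's exact test if expected counts are small, giving the risk difference and 95% CI. Report number of doses by arm. State that RSS is analysed as recorded whether or not ketamine was given, and is interpreted only beside the rescue result.

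Cost: text changes in two places, with no new data and no change to N. The ethics committee's letter requires a revised protocol to be submitted for approval before changes are implemented. Two secondary, unpowered p-values (RSS and ketamine) are added and should be labelled as such.

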## **HYPOTHESIS:**

Propofol infusion will cause less hemodynamics instability than sevoflurane.

## **MATERIAL AND METHOD:**

- **Study design:** Randomized Controlled trial study is used.
- **Study Setting:** Department of Anesthesiology, Sindh institute of urology and transplantation (SIUT).
- **Duration:** 6 months after approval from ethical review committee of SIUT.
- **Sample size:** Based on the previous estimate of hypotension in sevoflurane group was found in 33% of patients and 8.8% in propofol infusion group with power of 80% & 5% level of significance. A total no of 86 patients will be part of study, out of which 43 will be selected for each group. [11]

## **INCLUSION CRITERIA:**

- Patients between age group of 20-60 years
- Both male and female patients.
- ASA status I-II
- Elective ERCP procedure.

## **EXCLUSION CRITERIA:**

- Patients allergic to any study drug.
- ASA III-IV like Patients with uncontrolled DM, HTN and renal insufficiency.
- BMI over 36 KG/m^2 (Morbid obese)
- Sleep Apnea
- Gastroesophageal reflux disease (GERD)
- Pregnancy

## **DATA COLLECTION PROCEDURE**

This study will be conducted after approval of ethical committee of SIUT. For research 86 patients will be selected for the elective ERCP. Pre-operative assessment will be taken such as history of patients, general physical examination, systematic examination, and laboratory investigations will be part of assessment. Patients will be divided in two groups based on agents used for the research study. Both the groups will be induced by injection midazolam 0.06 mg/kg and injection nalbuphine 0.1 mg/kg . Anesthesia will be maintained in.....

**Group A** Sevoflurane inhalation to achieve MAC Amnesia 0.25%.

**Group B** Propofol infusion at 50 ug/Kg/min.

When Ramsay Sedation Scale **5** is achieved than surgeon will be allowed to insert endoscope. Inj **Ketamine** 0.5mg/kg will be used for Rescue sedation .Upon arrival in operation theatre standard monitoring which includes pulse oxymeter (SPO2), noninvasive blood pressure (NIBP), electrocardiogram (ECG) electrodes will be applied, and baseline readings will be recorded. After that venous access will be secured on a non-dominant hand by 20G IV cannula, i/v fluid (R/L or N/S) will then be started by 8 ml/kg/h and O2 will be given by nasal mask at 4 L/min. All baseline parameters will be taken, after that readings will be taken at 5 min, 10 min, 15 min,20 min and so on till procedure ends.

Complications such as respiratory depression, coughing, gagging, nausea and vomiting will be recorded during the procedure and treated accordingly. If SpO2 goes down below 92% for more than 10 seconds or patient develops apnea, it will be considered oxygen desaturation.

It will be managed by O2 inhalation and supporting airway. A heart rate under 40beats per minute will be considered bradycardia and it will be managed by inj Atropine 10 ug/Kg I/V. Mean arterial pressure level that is lower than 60 mmHg or 20% less than the baseline will be regarded as hypotension and it will be managed by fluid bolus or vasopressors.

Complications such as respiratory depression, coughing, gagging, nausea and vomiting will be recorded and treated accordingly. After the procedure, patient will be awakened and shifted to HDU.

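### Ketamine rescue has no stated trigger and no recorded dose time, so mean Ramsay score can hide or reverse a sedation difference between the regimens; rescue use should be a named outcome

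*Protocol*

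**What the plan says.** The protocol's Objective names sedation and haemodynamic change as the two things to be compared, and adds: "For sedation we use Ramsay Sedation score".

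Data Collection Procedure gives both groups midazolam and nalbuphine, then one maintenance setting per arm: "Sevoflurane inhalation to achieve MAC Amnesia 0.25"% for Group A and "Propofol infusion at 50 ug/Kg/min" for Group B. It describes no stepwise increase towards a sedation target. RSS 5 is the condition for inserting the endoscope. Ketamine "0.5mg/kg will be used for Rescue sedation"; the section does not say what prompts it.

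The complications form has a line headed "Ketamine used as Rescue Sedation", with yes, no and the number of doses. It has no field for the time of a dose. RSS is charted at baseline and every 5 minutes, with rows to 60 minutes.

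The analysis section lists "BMI, RSS, HR, SBP, DBP and MAP at 0,1,3,5,10 min" for mean and SD, and the SAP repeats this: "Mean and standard deviation will be computed for variable such as age, height, BMI, RSS". The t test is introduced with "For determining the differences in the hemodynamics mean unpaired", so it is assigned to haemodynamic means. No test is named for RSS. Neither document names ketamine use as an analysis variable or says how readings after ketamine are treated.

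**The concern.** Rescue is given to patients whose sedation is judged too light, and its purpose is to deepen it. The regimen that sedates less well should therefore collect more ketamine, and the ketamine raises its later RSS readings. A mean that pools readings before and after rescue is pulled towards the other arm, and past it if ketamine sedates more deeply than the assigned agent.

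Two gaps make this hard to undo at analysis. Without dose times, a rescued patient's readings cannot be divided into before and after. Without a common trigger, a difference in rescue counts may partly reflect when individual clinicians choose to give ketamine. At stake is the sedation half of the objective: similar mean RSS could be reported as similar sedation when one regimen needed more rescue to get there.

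**Working it through.** **The plan's own figure.** The only calculation in the documents is the sample size: hypotension 33% v 8.8%, 80% power, 5% significance, 43 per arm. Taking a two-sided test with pooled variance and no continuity correction:

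- mean proportion = (0.33 + 0.088)/2 = 0.209
- n = [1.96 × √(2 × 0.209 × 0.791) + 0.842 × √(0.33 × 0.67 + 0.088 × 0.912)]² / 0.242² ≈ 43.1, which rounds up to 44 per arm
- power with 43 per arm = 79.9%

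The figure reproduces to within one patient per arm. It concerns hypotension and does not bear on RSS.

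**Which readings are affected**

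| Readings | Effect of rescue |
|---|---|
| Any time, patient marked as not given ketamine | None |
| Named summaries (0, 1, 3, 5, 10 min), rescued patient | Only if ketamine was given by 10 min |
| 15 to 60 min, rescued patient | Affected once ketamine is given; collected, but not named for analysis |

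**Illustration of direction.** Every rate and score here is an assumption, because the documents give none.

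- Adequately sedated patients: RSS 4/5/6 in 10/70/20%, mean 5.1.
- Under-sedated patients before ketamine: RSS 3/4 in 30/70%, mean 3.7.
- The same patients after ketamine: mean 4.8 (lighter than the others), 5.1 (the same) or 5.5 (deeper).
- r₁ and r₂ are the rescue rates in the two arms; f is the share of rescued patients whose reading falls after ketamine.

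Gap in mean RSS (higher-rescue arm minus the other) = (r₁ − r₂) × [(1 − f) × 3.7 + f × post − 5.1].

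Example at 30% v 10% with f = 0: 0.20 × (3.7 − 5.1) = −0.28. With f = 1 and post = 5.5: 0.20 × (5.5 − 5.1) = +0.08.

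| Rescue rates | f = 0 | f = 0.5 (post 4.8 / 5.1 / 5.5) | f = 1 (post 4.8 / 5.1 / 5.5) |
|---|---|---|---|
| 20% v 10% | −0.14 | −0.085 / −0.07 / −0.05 | −0.03 / 0 / +0.04 |
| 30% v 10% | −0.28 | −0.17 / −0.14 / −0.10 | −0.06 / 0 / +0.08 |
| 35% v 10% | −0.35 | −0.21 / −0.175 / −0.125 | −0.075 / 0 / +0.10 |

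The exact zeros follow from setting the post-ketamine mean equal to 5.1.

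**A second, simpler model.** Assume a true difference of 0.5 RSS points without rescue, rescue only in the lighter arm, and ketamine adding 1 to 2 points. The observed difference is 0.5 − (share rescued × points added): 0.4 to 0.3 with 10% rescued, 0.3 to 0.1 with 20%, and 0.2 to −0.1 with 30%. The direction is the same.

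**Rescue use as an outcome.** This does not depend on when RSS is read. Take hypothetical counts of 13/43 v 4/43 rescued, about 30% v 9%:

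- difference = 0.302 − 0.093 = 0.209
- chi-square = 86 × (13 × 39 − 30 × 4)² / (43 × 43 × 17 × 69) = 5.94, p = 0.015
- Newcombe 95% CI 0.040 to 0.368

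Exact binomial power of the uncorrected two-sided 5% chi-square with 43 per arm is 26% at 20% v 10%, 67% at 30% v 10% and 83% at 35% v 10%.

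**The case against.** Much of the case on the other side is sound.

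- **A reader might infer that ketamine-free readings cannot be identified at all.** They can, for every patient marked as not given ketamine. In the example above that is 86 − 17 = 69 of 86 patients. The ambiguity is confined to rescued patients, although an analysis restricted to the rest would compare selected groups.
- **A reader might infer that the plan fails to measure the effect of each agent alone.** No post-induction score does that, because all patients receive midazolam and nalbuphine. The comparison is of two regimens, and RSS regardless of rescue is a legitimate description of them. It still needs rescue use beside it to be interpreted.
- **A reader might infer that a flawed test of RSS is planned.** None is named; as written, RSS is descriptive.
- **The named times end at 10 minutes.** This limits the problem to early rescue unless the later readings are used.
- **A trigger may be implied.** The rescue sentence directly follows the RSS 5 insertion rule, so failure to reach RSS 5 is a plausible reading before insertion. Nothing covers the period after it. The same section gives numeric thresholds for desaturation, bradycardia and hypotension, so a rescue threshold would match its style.
- **Delivery may be adjusted.** Sevoflurane is given to a target, which may involve changing the dial. That is adjustment to a MAC value, not to a sedation score.
- **The data are largely there.** Ketamine use and dose count are collected, a chi-square is planned, and the variable lists are open-ended. This makes the fix cheap. It does not supply a trigger, dose times or a rule for readings after rescue.

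**Conclusion.** The point holds within those limits. Sedation is a stated comparison, its measure can be altered by a rescue drug given without a stated common trigger, and in rescued patients the form cannot show which readings were altered. Mean RSS alone can therefore shrink or reverse a difference between the regimens.

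The size cannot be found from the documents. The range of −0.28 to +0.08 at 30% v 10% rests wholly on assumed rates and score distributions and on a single reading per patient; it shows direction only. The p value of 0.015 comes from invented counts and predicts nothing about this trial.

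It would go too far to conclude that the RSS data are unusable or that the main question is compromised. The hypothesis and the sample size concern haemodynamics and hypotension, and this point changes neither. It is a worthwhile, low-cost improvement to how the sedation comparison can be read.

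**What to change.** 1. **Protocol Data Analysis and SAP.** Name ketamine rescue (yes/no, from the existing form field) as a secondary sedation outcome. Compare it between arms by the planned chi-square, with the difference and its 95% CI, and report the number of doses by arm.
2. **Data Collection Procedure.** State one ketamine trigger for both arms, for example failure to reach or hold a stated RSS. The clinicians should choose the threshold.
3. **Form.** Add the time of each ketamine dose. Report mean RSS descriptively, with post-ketamine readings identified.

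A wider composite, such as reaching RSS 5 and completing the procedure with no ketamine, change of agent or stop for inadequate sedation, is optional and not needed to repair the defect.

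The cost is one form field (repeated per dose), a sentence on the trigger and a few sentences of analysis. The ethics approval letter in the SAP file requires a revised protocol to be approved before changes are used. The new outcome has good power only for large differences (the 26%, 67% and 83% above). No extra patients are needed. If the form can no longer change, step 1 can still be done from the existing field, with the caveat that without a common trigger the counts may partly reflect clinician habit.

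### The forms capture desaturation only when there is apnoea: an SpO2 fall without apnoea, and respiratory depression short of apnoea, have no field

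*Protocol*

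**What the plan says.** The protocol's DATA COLLECTION PROCEDURE states: "Complications such as respiratory depression, coughing, gagging, nausea and vomiting will be recorded during the procedure and treated accordingly". It repeats the commitment in shorter form at the end of the section. It gives no definition of respiratory depression. It does define desaturation, with two limbs: if SpO2 "goes down below 92% for more than 10 seconds or patient develops apnea, it will be considered oxygen desaturation". The next sentence gives the treatment (oxygen and airway support). Bradycardia and hypotension follow in the same limit-then-treatment style.

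The form headed "COMPLICATION DURING AND AFTER ERCP" has four yes/no complication rows: apnoea, cough, gagging and "POST-OPERATIVE NAUSEA AND VOMITING". Its other fields are ketamine rescue and recovery time.

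The PERFORMA chart has a "Respiratory Monitoring" block with SpO2, respiratory rate and end-tidal CO2. Each has one cell at baseline and one every 5 minutes to 60 minutes. There is no field for the lowest value, for duration, or for events between readings.

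The protocol's DATA ANALYSIS section says that "post op complications like gagging, PONV, Apnea and cough will be presented as frequencies and percentages", and that a chi-square test will compare the groups. The SAP repeats this almost word for word. Neither names desaturation or respiratory depression.

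**The concern.** One complication that the protocol says will be recorded, and one respiratory event that it defines numerically, have no field of their own on the form that holds complications. The apnoea row catches desaturation by the apnoea limb. It does not catch a patient who keeps breathing, or whose airway is partly obstructed, while SpO2 falls.

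The INTRODUCTION says that with propofol "apnea, airway obstruction, hypoxemia and/or hypotension can result", so the protocol itself lists hypoxaemia and airway obstruction separately from apnoea. A trial of two sedatives taken to Ramsay 5 with mask oxygen would be expected to report both. If a brief fall in SpO2 is not noted when it happens, nothing that the documents name as recorded allows it to be recovered at analysis. What is at stake is the completeness of the respiratory safety comparison between arms.

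**Working it through.** **Step 1. The plan's own figure.** The only related number is the sample size, and it is not in dispute. With hypotension at 33% v 8.8%, two-sided 5%, 80% power, and pooled variance without continuity correction:

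n = [1.96·√(2·0.209·0.791) + 0.842·√(0.33·0.67 + 0.088·0.912)]² / 0.242² = 43.1, or 44 after rounding up.

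The plan states 43, at which power is 79.9%. The figure is reproduced and does not depend on desaturation.

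**Step 2. Text against forms.**

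| Event in DATA COLLECTION PROCEDURE | Row on complication form | Named in DATA ANALYSIS / SAP |
|---|---|---|
| Coughing | Yes | Yes |
| Gagging | Yes | Yes |
| Nausea and vomiting | Yes (one shared row) | Yes |
| Desaturation, apnoea limb | Yes (apnoea row) | Yes (as apnoea) |
| Desaturation, SpO2 limb | No | No |
| Respiratory depression | No (apnoea row may cover part) | No |

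Of the five complications listed as recorded, four have a place on the form and respiratory depression does not.

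**Step 3. Can the 5-minute chart fill the gap?** The SpO2 limb needs a fall lasting more than 10 s. One spot value shows a level and no duration, so even a charted value under 92% does not establish the event. A fall between readings leaves no trace. Respiratory rate and end-tidal CO2 are charted, but without a threshold they cannot be turned into respiratory depression. This step needs no assumed rates.

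**Step 4. Illustration only.** The documents give no desaturation rate or episode length. Assume that a fraction p of 43 patients have one non-apnoeic episode of L seconds, with timing unrelated to the readings. Then:

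- chance that a reading falls inside the episode = L/300
- true patients per arm = 43·p
- patients with a charted low value = 43·p·L/300
- chance that an arm's chart shows none = (1 − p·L/300)^43

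| p | L | L/300 | True | Charted | Chance of none |
|---|---|---|---|---|---|
| 10% | 10 s (lower bound) | 3.3% | 4.3 | 0.14 | 87% |
| 20% | 30 s | 10% | 8.6 | 0.86 | 42% |
| 30% | 60 s | 20% | 12.9 | 2.58 | 7% |
| 30% | 120 s | 40% | 12.9 | 5.16 | 0.4% |

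The result depends heavily on L, and repeat episodes in a patient would raise capture.

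**Step 5. What a box would give.** Assume 4/43 in each arm. The Wilson 95% limits for 4/43 = 9.3% are 3.7% and 21.6%. The Newcombe half-width is √[(9.3 − 3.7)² + (21.6 − 9.3)²] ≈ 13.5 percentage points.

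**The case against.** The strongest reply is that the form and the named analysis agree. The four complications named in DATA ANALYSIS are exactly the four rows on the form, so the comparison as named is not short of data. The desaturation sentence sits beside its treatment and can fairly be read as a treatment trigger; nothing expressly lists desaturation as a recorded outcome. The objective and hypothesis concern sedation and haemodynamics. All of this stands, and it keeps the point small. It does not dispose of respiratory depression, which is expressly to be recorded and has no field.

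A reader might infer several stronger things that the documents do not support:

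- **That desaturation is not captured at all.** The definition includes apnoea, and the form has an apnoea row.
- **That the statistical test is missing.** The complication list is open-ended and the chi-square test could take further events. The gap is in data capture.
- **That the trial will miss most of its desaturations by counting from the chart.** Nothing in the plan proposes such a count, and the risks and durations in Step 4 are assumed.
- **That desaturation is handled worse than bradycardia and hypotension in every respect.** Those two have no row either, and 5-minute readings miss brief episodes of both. Only the duration requirement sets desaturation apart: the other two can be judged from a single charted reading.

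**Conclusion.** The point holds in a limited form. With the forms used as written, the trial cannot report or compare SpO2 desaturation without apnoea, or respiratory depression short of apnoea. This follows from the text of the definition, the rows of the form and the chart's reading interval, and rests on no assumed rate. It takes the complication form and the chart as the complete record, since the documents name no other.

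The size of the loss cannot be stated, because the documents give no desaturation rate or duration; the capture figures above only illustrate. No direction of difference between arms is implied. A reader might go further and doubt the main result, but the sample size, the haemodynamic and sedation results and the comparisons of apnoea, cough, gagging and PONV do not use the missing item. It is an inexpensive improvement to safety reporting, worth making but not essential.

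**What to change.** 1. Add one yes/no box to the complication form: SpO2 under 92% lasting longer than 10 s, with or without apnoea. It should be ticked at the time from the oximeter.
2. In the protocol's DATA ANALYSIS section and in the SAP, name this event among the complications compared by arm. Show the apnoea and SpO2 limbs separately.
3. For respiratory depression, choose one of two courses. Either state that the existing desaturation definition, apnoea included, is its operational definition, so that no second box is needed; or add a box with a stated threshold.
4. For patients treated before the box exists, report the event as not collected. A blank must not be read as No.

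The cost is one box (two if respiratory depression gets its own threshold) and a line or two of text. Pulse oximetry is already required, so no patients, visits or equipment are added. The ethics approval letter filed with the SAP says "you must submit a revised protocol to the SIUT-ERC for approval before implementing the changes", so approval must come first. The comparison will be imprecise at 43 per arm and should be read through its confidence interval.
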